#### **5.3.5.6 Abnormal Vital Sign Values**

Not every vital sign abnormality qualifies as an adverse event. A vital sign result must be reported as an adverse event if it meets any of the following criteria:

- Is accompanied by clinical symptoms

- Results in a change in study treatment (e.g., dosage modification, treatment interruption, or treatment discontinuation)
- Results in a medical intervention or a change in concomitant therapy
- Is clinically significant in the investigator's judgment

It is the investigator's responsibility to review all vital sign findings. Medical and scientific judgment should be exercised in deciding whether an isolated vital sign abnormality should be classified as an adverse event.

If a clinically significant vital sign abnormality is a sign of a disease or syndrome (e.g., high blood pressure), only the diagnosis (i.e., hypertension) should be recorded on the Adverse Event eCRF.

Observations of the same clinically significant vital sign abnormality from visit to visit should only be recorded once on the Adverse Event eCRF (see Section 5.3.5.4 for details on recording persistent adverse events).

### **5.3.5.7      Abnormal Liver Function Tests**

The finding of an elevated ALT or AST ( $>3 \times$  baseline value) in combination with either an elevated total bilirubin ( $>2 \times$  ULN) or clinical jaundice in the absence of cholestasis or other causes of hyperbilirubinemia is considered to be an indicator of severe liver injury (as defined by Hy's Law). Therefore, investigators must report as an adverse event the occurrence of either of the following:

- Treatment-emergent ALT or AST  $>3 \times$  baseline value in combination with total bilirubin  $>2 \times$  ULN (of which  $\geq 35\%$  is direct bilirubin)
- Treatment-emergent ALT or AST  $>3 \times$  baseline value in combination with clinical jaundice

The most appropriate diagnosis or (if a diagnosis cannot be established) the abnormal laboratory values should be recorded on the Adverse Event eCRF (see Section 5.3.5.2) and reported to the Sponsor immediately (i.e., no more than 24 hours after learning of the event), either as a serious adverse event or an adverse event of special interest (see Sections 5.2.2 and 5.2.3).

### **5.3.5.8      Deaths**

All deaths that occur during the protocol-specified adverse event reporting period (see Section 5.3.1), regardless of relationship to study drug, must be recorded on the Adverse Event eCRF and immediately reported to the Sponsor (see Section 5.4.2). This includes death attributed to progression of BC.

Death should be considered an outcome and not a distinct event. The event or condition that caused or contributed to the fatal outcome should be recorded as the single medical concept on the Adverse Event eCRF. Generally, only one such event should be reported. If the cause of death is unknown and cannot be ascertained at the time of

reporting, "**unexplained death**" should be recorded on the Adverse Event eCRF. If the cause of death later becomes available (e.g., after autopsy), "unexplained death" should be replaced by the established cause of death. The term "**sudden death**" should not be used unless combined with the presumed cause of death (e.g., "sudden cardiac death").

If the death is attributed to progression of breast cancer, "breast cancer progression" should be recorded on the Adverse Event eCRF and the details (e.g., clinical course, clinical findings, cause of death as per the death certificate) should be recorded in the Serious Adverse Event detail field.

Deaths that occur after the adverse event reporting period should be reported as described in Section [5.6](#).

#### **5.3.5.9 Preexisting Medical Conditions**

A preexisting medical condition is one that is present at the screening visit for this study. Such conditions should be recorded on the General Medical History and Baseline Conditions eCRF.

A preexisting medical condition should be recorded as an adverse event only if the frequency, severity, or character of the condition worsens during the study. When recording such events on the Adverse Event eCRF, it is important to convey the concept that the preexisting condition has changed by including applicable descriptors (e.g., "more frequent headaches").

#### **5.3.5.10 Lack of Efficacy or Worsening of Breast Cancer**

Events that are clearly consistent with the expected pattern of progression of the underlying disease (e.g., new lesion, increase in target- or non-target-lesions) should not be recorded as adverse events. These data will be captured as efficacy assessment data only. In most cases, the expected pattern of progression will be based on RECIST v1.1. In rare cases, the determination of clinical progression will be based on symptomatic deterioration. However, every effort should be made to document progression through use of objective criteria. If there is any uncertainty as to whether an event is due to disease progression, it should be reported as an adverse event.

#### **5.3.5.11 Hospitalization or Prolonged Hospitalization**

Any adverse event that results in hospitalization (i.e., inpatient admission to a hospital) or prolonged hospitalization should be documented and reported as a serious adverse event (per the definition of serious adverse event in Section [5.2.2](#)), except as outlined below.

An event that leads to hospitalization under the following circumstances should not be reported as an adverse event or a serious adverse event:

- Hospitalization for respite care

- Hospitalization for a preexisting condition, provided that all of the following criteria are met:
  - The hospitalization was planned prior to the study or was scheduled during the study when elective surgery became necessary because of the expected normal progression of the disease
  - The patient has not experienced an adverse event
- Hospitalization due solely to progression of the underlying cancer (e.g. tumor pain or failure to thrive that require in-patient care)

An event that leads to hospitalization under the following circumstances is not considered to be a serious adverse event, but should be reported as an adverse event instead:

- Hospitalization that was necessary because of patient requirement for outpatient care outside of normal outpatient clinic operating hours

#### **5.3.5.12 Adverse Events Associated with an Overdose or Error in Drug Administration**

An overdose is the accidental or intentional use of a drug in an amount higher than the dose being studied. An overdose or incorrect administration of study treatment is not itself an adverse event, but it may result in an adverse event. All adverse events associated with an overdose or incorrect administration of study drug should be recorded on the Adverse Event eCRF. If the associated adverse event fulfills seriousness criteria, the event should be reported to the Sponsor immediately (i.e., no more than 24 hours after learning of the event; see Section [5.4.2](#)).

No safety data related to overdosing of DHES0815A are available.

### **5.4 IMMEDIATE REPORTING REQUIREMENTS FROM INVESTIGATOR TO SPONSOR**

Certain events require immediate reporting to allow the Sponsor to take appropriate measures to address potential new risks in a clinical trial. The investigator must report such events to the Sponsor immediately; under no circumstances should reporting take place more than 24 hours after the investigator learns of the event. The following is a list of events that the investigator must report to the Sponsor within 24 hours after learning of the event, regardless of relationship to study drug:

- Serious adverse events (defined in Section [5.2.2](#); see Section [5.4.2](#) for details on reporting requirements)
- Adverse events of special interest (defined in Section [5.2.3](#); see Section [5.4.2](#) for details on reporting requirements)
- DLTs during the DLT assessment window (defined in Section [5.2.4](#); see Section [5.4.2](#) for details on reporting requirements)
- Pregnancies (see Section [5.4.3](#) for details on reporting requirements)

The investigator must report new significant follow-up information for these events to the Sponsor immediately (i.e., no more than 24 hours after becoming aware of the information). New significant information includes the following:

- New signs or symptoms or a change in the diagnosis
- Significant new diagnostic test results
- Change in causality based on new information
- Change in the event's outcome, including recovery
- Additional narrative information on the clinical course of the event

Investigators must also comply with local requirements for reporting serious adverse events to the local health authority and IRB/EC.

#### **5.4.2        Reporting Requirements for Serious Adverse Events, Adverse Events of Special Interest and Dose-Limiting Toxicities**

##### **5.4.2.1      Events That Occur prior to Study Drug Initiation**

After informed consent has been obtained but prior to initiation of study drug, only serious adverse events caused by a protocol-mandated intervention should be reported. The paper Clinical Trial Serious Adverse Event/Adverse Event of Special Interest Reporting Form provided to investigators should be completed and submitted to the Sponsor or its designee immediately (i.e., no more than 24 hours after learning of the event) by faxing the form using the fax number provided to investigators.

Serious adverse events should be reported by fax to PPD.

#### **5.4.2.2 Events That Occur after Study Drug Initiation**

After initiation of study drug, serious adverse events and adverse events of special interest will be reported until 42 days after the last dose of study drug or until the patient is lost to follow-up, withdraws consent, initiates another anti-cancer therapy, or study discontinuation/termination, whichever occurs first. DLTs will be reported during the DLT assessment window. Investigators should record all case details that can be gathered immediately (i.e., within 24 hours after learning of the event) on the Adverse Event eCRF and submit the report via the EDC system. A report will be generated and sent to Safety Risk Management by the EDC system.

In the event that the EDC system is unavailable, the paper Clinical Trial Serious Adverse Event/Adverse Event of Special Interest Reporting Form provided to investigators should be completed and submitted to the Sponsor or its designee immediately (i.e., no more than 24 hours after learning of the event) by faxing the form using the fax number provided to investigators in Section [5.4.2.1](#). Once the EDC system is available, all information will need to be entered and submitted via the EDC system.

Instructions for reporting serious adverse events that occur after the adverse event reporting period are provided in Section [5.6](#).

#### **5.4.3 Reporting Requirements for Pregnancies**

##### **5.4.3.1 Pregnancies in Female Patients**

Female patients of childbearing potential will be instructed to immediately inform the investigator if they become pregnant during the study or within 8.5 months after the last dose of study drug. A Clinical Trial Pregnancy Reporting Form should be completed and submitted to the Sponsor or its designee immediately (i.e., no more than 24 hours after learning of the pregnancy) by faxing the form using the fax number provided to investigators in Section [5.4.2.1](#). Pregnancy should not be recorded on the Adverse Event eCRF. The investigator should discontinue study drug and counsel the patient, discussing the risks of the pregnancy and the possible effects on the fetus. Monitoring of the patient should continue until conclusion of the pregnancy. Any serious adverse events associated with the pregnancy (e.g., an event in the fetus, an event in the mother during or after the pregnancy, or a congenital anomaly/birth defect in the child) should be reported on the Adverse Event eCRF. In addition, the investigator will submit a Clinical Trial Pregnancy Reporting Form when updated information on the course and outcome of the pregnancy becomes available.

##### **5.4.3.2 Pregnancies in Female Partners of Male Patients**

Male patients will be instructed through the Informed Consent Form to immediately inform the investigator if their partner becomes pregnant during the study or within 5.5 months after the last dose of study drug. A Clinical Trial Pregnancy Reporting Form should be completed and submitted to the Sponsor or its designee immediately (i.e., no more than 24 hours after learning of the pregnancy) by faxing the form using the fax number provided to investigators in Section [5.4.2.1](#). Attempts should be made to

collect and report details of the course and outcome of any pregnancy in the partner of a male patient exposed to study drug. When permitted by the site, the pregnant partner would need to sign an Authorization for Use and Disclosure of Pregnancy Health Information to allow for follow-up on her pregnancy. If the authorization has been signed, the investigator should submit a Clinical Trial Pregnancy Reporting Form when updated information on the course and outcome of the pregnancy becomes available. An investigator who is contacted by the male patient or his pregnant partner may provide information on the risks of the pregnancy and the possible effects on the fetus, to support an informed decision in cooperation with the treating physician and/or obstetrician.

#### **5.4.3.3 Congenital Anomalies/Birth Defects and Abortions**

Any congenital anomaly/birth defect in a child born to a female patient exposed to study drug or the female partner of a male patient exposed to study drug should be classified as a serious adverse event, recorded on the Adverse Event eCRF, and reported to the Sponsor immediately (i.e., no more than 24 hours after learning of the event; see Section 5.4.2). Any abortion should be reported in the same fashion (as the Sponsor considers abortions to be medically significant).

### **5.5 FOLLOW-UP OF PATIENTS AFTER ADVERSE EVENTS**

#### **5.5.1 Investigator Follow-Up**

The investigator should follow each adverse event until the event has resolved to baseline grade or better, the event is assessed as stable by the investigator, the patient is lost to follow-up, or the patient withdraws consent. Every effort should be made to follow all serious adverse events that are considered to be related to study drug or trial-related procedures until a final outcome can be reported.

During the study period, resolution of adverse events (with dates) should be documented on the Adverse Event eCRF and in the patient's medical record to facilitate source data verification.

All pregnancies reported during the study should be followed until pregnancy outcome.

#### **5.5.2 Sponsor Follow-Up**

For serious adverse events, adverse events of special interest, and pregnancies, the Sponsor or a designee may follow up by telephone, fax, and/or a monitoring visit to obtain additional case details and outcome information (e.g., from hospital discharge summaries, consultant reports, autopsy reports) in order to perform an independent medical assessment of the reported case.

### **5.6 ADVERSE EVENTS THAT OCCUR AFTER THE ADVERSE EVENT REPORTING PERIOD**

The Sponsor should be notified if the investigator becomes aware of any serious adverse event that occurs after the end of the adverse event reporting period (defined as

42 days after the last dose of study drug or until the patient is lost to follow-up, withdraws consent, initiates another anti-cancer therapy, or study discontinuation/termination, whichever occurs first) if the event is believed to be related to prior study drug treatment. These events should be reported through use of the Adverse Event eCRF. However, if the EDC system is not available, the investigator should report these events directly to the Sponsor or its designee, by faxing the paper Clinical Trial Serious Adverse Event/Adverse Event of Special Interest Reporting Form using the fax number provided to investigators.

## **5.7           EXPEDITED REPORTING TO HEALTH AUTHORITIES, INVESTIGATORS, INSTITUTIONAL REVIEW BOARDS, AND ETHICS COMMITTEES**

The Sponsor will promptly evaluate all serious adverse events and adverse events of special interest against cumulative product experience to identify and expeditiously communicate possible new safety findings to investigators, IRBs, ECs, and applicable health authorities based on applicable legislation.

To determine reporting requirements for single adverse event cases, the Sponsor will assess the expectedness of these events using the DHES0815A Investigator's Brochure as a reference document.

The Sponsor will compare the severity of each event and the cumulative event frequency reported for the study with the severity and frequency reported in the applicable reference document.

Reporting requirements will also be based on the investigator's assessment of causality and seriousness, with allowance for upgrading by the Sponsor as needed.

## **6.           STATISTICAL CONSIDERATIONS AND ANALYSIS PLAN**

The objective of the dose escalation is to determine the MTD/MAD and RP2D of DHES0815A.

If the safety and PK profile seen in the dose-escalation portion of the study is deemed to be favorable to justify further continuation of the study, expansion cohorts will be enrolled to further confirm safety and tolerability and to assess preliminary evidence of anti-tumor activity and exploratory pharmacodynamic markers of response.

The final analysis will be based on patient data collected through patient discontinuation or study discontinuation, whichever occurs first. All analyses will be based on the safety-evaluable population. All summaries will be presented according to the assigned dose level and cohort. In general, data will be summarized as warranted, and listings will be used in place of tables when the sample sizes are small. Continuous variables will be summarized using means, standard deviations, median, and ranges; categorical variables will be summarized using counts and percentages.

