Patients in this study will be initially assessed for eligibility during the screening period (lasting  $\leq$  28 days). Following confirmation of eligibility, patients will receive DHES0815A by IV infusion on the first day of every cycle. A detailed PK evaluation will be performed during Cycle 1 and more limited PK assessments thereafter. Patients will be evaluated weekly by physical examination and by blood collections for routine hematologic and metabolic laboratory assessments for the first four cycles of DHES0815A treatment during dose escalation, the first two cycles during dose expansion, and less frequently thereafter. Cardiac ejection fraction (left ventricular ejection fraction [LVEF]) will be monitored by transthoracic echocardiogram (ECHO) or multiple-gated acquisition scan (MUGA) at baseline and in the last week (Days 15–21) of Cycles 1, 2, 4, and 6, and then after every four cycles thereafter. Ophthalmic examinations (best corrected visual acuity [BCVA] and anterior segment slit lamp examination with fluorescein) to monitor for visual and/or corneal changes will occur at baseline and during the last week (Days 15–21) of Cycles 2, 4, and 6, and every four cycles thereafter. Tumor assessment will occur at baseline and during the last week (Days 15–21) of every even-numbered cycle until Cycle 8 (i.e., at Cycles 2, 4, 6, and 8) and at every three cycles thereafter (i.e., at Cycles 11, 14, 17, etc.) until discontinuation or study termination.

Adverse events will be graded according to the National Cancer Institute Common Terminology Criteria for Adverse Events, Version 4.0 (NCI CTCAE v4.0). Patients deriving clinical benefit may be offered continued treatment with DHES0815A until disease progression or intolerable toxicity at the discretion of the investigator (see Section 3.1.1.4).

Disease status will be assessed using the Response Evaluation Criteria in Solid Tumors, Version 1.1 (RECIST v1.1) (Eisenhauer et al. 2009; see [Appendix 3](#)). Tumor status will be categorized as a complete response (CR), partial response (PR), stable disease, or progressive disease (PD), per RECIST v1.1. Objective response should be confirmed by repeat physical examination or image-based evaluation  $\geq$  4 weeks after the initial documentation, per RECIST v1.1 (see [Appendix 3](#)).

Blood samples will be collected for assessment of molecular and genetic biomarkers at baseline and end of study.

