A detailed schedule of activities is provided in [Appendix 1](#) and [Appendix 2](#).

[REDACTED] . Patients enrolled in Cohorts 1–5 (0.6 mg/kg Q3W, 1.2 mg/kg Q3W, 2.4 mg/kg Q3W, 4.0 mg/kg Q3W, and 6.0 mg/kg Q3W, respectively) may not receive a dose higher than 2.4 mg/kg Q3W, [REDACTED]

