### **3.1.1.3      Intrapatient Dose Escalation**

To minimize the exposure of patients to suboptimal doses and to maximize the collection of information at relevant doses, patients may progressively escalate from their current dose of DHES0815A to the highest dose level tolerated by completed cohorts. Patients will need to complete at least three cycles at their originally assigned DHES0815A dose level, as well as at each of the subsequent dose levels, prior to any further dose escalation.

Once the MTD is declared and the RP2D is determined, patients who remain in the study and continue to tolerate the study drug may escalate their dose to the RP2D level or the dose level below the RP2D under their current dosing schedule. The RP2D will be at or below the MTD (or MAD) and determined by the totality of data, including DLTs, safety, activity, and PK data (see Section [3.1.1.2](#)).

All intrapatient dose-escalation decisions will be made by the Sponsor in consultation with the participating investigators and will include assessment of safety data within the treatment cohorts, as well as the totality of the safety data.

*For patients in Cohorts 1–5, please also refer to Section [3.1](#).*

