### **3.1.1.4      Continuation of DHES0815A (Cycles $\geq 2$ )**

Patients without a DLT during the DLT assessment window will be eligible to receive additional infusions of DHES0815A at the same dose level at which they were enrolled or at an increased dose as detailed in Section [3.1.1.3](#) (the day of infusion being Day 1 of each cycle), provided that they meet the following criteria for acceptable toxicity and ongoing clinical benefit:

- Acceptable toxicity: All adverse events experienced with prior infusions that were not attributed to constitutional symptoms of the patient's cancer or intercurrent illness must have decreased to Grade 1 or baseline grade on or before the day of the next infusion.

Exceptions on the basis of ongoing clinical benefit may be allowed after a careful assessment and discussion of benefit versus risk with the patient by the investigator and approval from the Medical Monitor. In addition, delay of therapy because of toxicities not attributed to study drug may not require discontinuation

from the study but must be approved by the Medical Monitor. Dose modifications are described in Section 5.1.2.1.

- Ongoing clinical benefit: Patients must demonstrate improvement/stabilization in tumor burden, according to the RECIST v1.1 ([Appendix 3](#)) or demonstrate clinical signs or symptoms of benefit, as judged by the investigator, independent of RECIST.

All tumors assessed at screening must be documented and re-assessed at each subsequent tumor evaluation (see [Appendix 1](#) for tumor assessment schedule). For each patient, the same imaging modality should be used throughout the study.

*For patients in Cohorts 1–5, please also refer to Section 3.1.*

Women of childbearing potential will need to undergo a urine pregnancy test prior to each DHES0815A cycle (patients whose breast tumor produces human chorionic gonadotropin [hCG] and were confirmed not to be pregnant prior to enrollment should be monitored with serum pregnancy tests rather than urine pregnancy tests prior to each cycle of study treatment). If a urine pregnancy test result is positive, patient dosing will be postponed until the result is confirmed by a serum pregnancy test. Patients who are pregnant must permanently discontinue study treatment.

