#### **4.5.8        Cardiac Assessments with Echocardiography or MUGA**

ECHO is the preferred method of assessment of LVEF, although MUGA scan is also accepted. All efforts should be made to use the same method and the same facilities throughout the entire study for each patient and to have the same assessor for each.

LVEF is to be assessed at screening, during the last week (Days 15–21) of Cycles 1, 2, 4, and 6, and then every four cycles thereafter, or as clinically indicated. Please refer to [Appendix 1](#) for the schedule of cardiac assessments.

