### 6.4.1 Adverse Events

All adverse events occurring on or after treatment on Day 1 will be summarized by mapped term, appropriate thesaurus levels, and NCI CTCAE v4.0 toxicity grade.

All adverse events reported during the adverse event reporting period will be considered as treatment-emergent adverse events. Incidence rates will be summarized with frequency and percentage by mapped term, with all patients treated as the denominator, unless otherwise specified. In addition, adverse event incidence rates will also be summarized by severity and relationship to study drug. Treatment-related adverse events are those judged by the Investigator to be at least possibly related to the study drug.

Safety will be assessed through summaries of adverse events, changes in laboratory test results, and DHES0815A exposure. All patients who receive study treatment on Cycle 1, Day 1 will be included in the analyses.

Adverse event data will be listed by patient number and study day. Serious adverse events, including deaths, will be listed separately and will be summarized.

Relevant laboratory and vital sign (pulse rate, blood pressure, and temperature) data will be displayed by time, with NCI CTCAE v4.0 Grades 3 and 4 values identified, where appropriate. Additionally, all laboratory data will be summarized by NCI CTCAE v4.0.

Safety data will be accumulated up to the end of the patient's treatment period.

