## **6.7 IMMUNOGENICITY ANALYSES**

Patients are considered to have treatment-induced ADA responses if they are ADA negative at baseline and develop an ADA response following DHES0815A administration. Patients are considered to have treatment-enhanced ADA if they are ADA positive at baseline and the titer of one or more postbaseline samples is at least 4-fold greater than baseline titer (i.e.,  $\geq 0.60$  titer units) following study drug administration. ADA incidence will be determined from the patients with treatment-induced and treatment-enhanced ADA.

Patients are considered to be negative for ADAs if they are ADA negative at all timepoints. Patients are considered to be treatment unaffected if they are ADA positive at baseline but do not have any postbaseline samples with a titer that is at least 4-fold

greater than the titer of the baseline sample. ADA prevalence will be determined from all patients with ADA-positive responses at baseline.

The immunogenicity analysis population will consist of all patients with at least one ADA assessment. Patients will be grouped according to treatment received or, if no treatment is received prior to study discontinuation, according to treatment assigned.

The relationship between ADA status and safety, efficacy, PK, activity, and biomarker endpoints will be analyzed and reported via descriptive statistics, as data allow.

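### All summaries are filed under the assigned dose, although intrapatient escalation can raise the received dose from Cycle 4; add supplementary safety summaries by dose received

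*Combined protocol and SAP*

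**What the plan says.** Section 6, and the Synopsis under Primary Analysis, set one grouping rule: "All summaries will be presented according to the assigned dose level and cohort".

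Section 3.1.1.3 permits intrapatient escalation up to the highest level that completed cohorts have tolerated, after a waiting period: "Patients will need to complete at least three cycles at their originally assigned DHES0815A dose level", and again at each later level. A further route, to the RP2D or the level below it, opens once the RP2D is set. Section 3.1.1.4 says that patients without a DLT may go on receiving infusions "at the same dose level at which they were enrolled or at an increased dose". Section 3.1 lists Cohorts 1 to 5 as 0.6, 1.2, 2.4, 4.0 and 6.0 mg/kg every three weeks and limits all five to 2.4 mg/kg. Under that limit, only Cohorts 1 and 2 among the five can rise above their own label.

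Section 5.3.1 collects adverse events until 42 days after the last dose. Section 6.4.1 then says: "Incidence rates will be summarized with frequency and percentage by mapped term, with all patients treated as the denominator, unless otherwise specified". No rule ties an event to the dose being given at onset. Section 6.4 lists drug administration and flags dose modifications. Section 6.7 uses different words for the immunogenicity analysis: "Patients will be grouped according to treatment received or, if no treatment is received prior to study discontinuation, according to treatment assigned".

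**The concern.** Adverse events, laboratory changes and LVEF are endpoints of the primary objective (Section 2, Table 1), and the final tables are meant to describe them by dose. If an escalated Cohort 1 patient has an event while receiving 1.2 or 2.4 mg/kg, the rule in Section 6 counts it in the 0.6 mg/kg column. The low-dose column then carries toxicity from a higher dose, and the higher-dose column loses both the event and the time at risk.

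This also works against the protocol's own reason for allowing escalation, which Section 3.1.1.3 gives as gaining more information at relevant doses. That information would appear in the summaries only under the starting dose.

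**Working it through.** The plan gives no figure on this point to reproduce. The check is whether the mismatch can arise under the plan's own rules, and how large it can be.

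**Inputs.** 21-day cycles and the dose ladder (Section 3.1); at least three cycles per level (Section 3.1.1.3); a one-day stagger for the first patient and cohorts of 3 to 6 (Section 3.1.1); 24 to 30 patients in escalation (Section 6.1.1); LVEF in the last week "of Cycles 1, 2, 4, and 6, and then every four cycles thereafter, or as clinically indicated" (Section 4.5.8); tumour scans in the last week of Cycles 2, 4, 6 and 8 (Section 3.1).

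**Earliest escalation.** Cycle 4 Day 1 is Day 3 × 21 + 1 = 64. A second step at Cycle 7 Day 1 is Day 6 × 21 + 1 = 127.

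**Whether the next cohorts can be complete by then.** Assume three patients per cohort, no DLT, no enrolment gaps and no meeting time.

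| Cohort | Starts (Day) | Last DLT window ends (Day) |
|---|---|---|
| 1 (0.6 mg/kg) | 1–2 | 22 |
| 2 (1.2 mg/kg) | 23–24 | 44 |
| 3 (2.4 mg/kg) | 45–46 | 66 |

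The first Cohort 1 patient reaches Cycle 4 on Day 64, after Day 44, and Cycle 7 on Day 127, after Day 66. The first Cohort 2 patient reaches Cycle 4 on Day 23 + 63 = 86, also after Day 66. So the rules permit the mismatch. Slower enrolment only delays it.

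**Received over assigned dose, earliest stepwise escalation.**
- Cohort 1: 1.2/0.6 = 2 from Cycle 4; 2.4/0.6 = 4 from Cycle 7. Over 8 cycles: 3 × 0.6 + 3 × 1.2 + 2 × 2.4 = 10.2 mg/kg against 8 × 0.6 = 4.8, a ratio of 2.1.
- Cohort 2: 2.4/1.2 = 2 from Cycle 4. Over 8 cycles: 3 × 1.2 + 5 × 2.4 = 15.6 mg/kg against 8 × 1.2 = 9.6, a ratio of 1.6.

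**Share of one such patient's data above the label.**
- Cycles: 3 of 6 (50%) or 6 of 9 (67%).
- LVEF assessments to Cycle 6: 2 of 4 (Cycles 4 and 6).
- Scans to Cycle 8: 3 of 4 (Cycles 4, 6 and 8). Only a response first seen at the Cycle 2 scan is certain to precede escalation.

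**Number of patients.** With three per cohort, Cohorts 1 and 2 hold 2 × 3 = 6 patients: 6/30 = 20%, 6/24 = 25%. Each must also meet the toxicity and benefit criteria of Section 3.1.1.4 and have a Sponsor decision to escalate, so 6 is the most these two cohorts can give at that size.

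**Effect on a column.** Where a percentage is tabulated, one patient's event moves it by 1/6 = 17 points in a cohort of six, or 1/3 = 33 points in a cohort of three.

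**The case against.** The best reply is that grouping by assigned dose is an accepted convention and that the raw material is already there. Section 6 allows listings in place of tables when samples are small, which describes cohorts of 3 to 6. Section 6.4.1 lists adverse events by patient and study day, Section 6.4 lists dosing with modifications flagged, and Table 1 includes dose intensity and exploratory exposure relationships. A reader could work out the dose at onset for a handful of patients.

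Most of that stands, and it is why the assigned-dose tables should stay primary. It does not close the gap. None of these items gives incidence or time at risk by dose received. The flag may not even cover escalation: Section 3.1.1.4 refers dose modifications to Section 5.1.2.1, which deals with reductions and delays.

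Several stronger readings are tempting and are not supported:

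- A reader might infer that DLT counts, the MTD or the RP2D are distorted. DLTs are counted in Cycle 1, before any escalation. Section 3.1.1.2 has dose-administration data reviewed before dose-escalation decisions, and Section 4.2 adds cumulative safety data.
- A reader might take six patients in each of Cohorts 1 and 2 and conclude that half of a 24-patient stage is exposed. Under Section 3.1.1.2 a DLT limits later increases to 50%, whereas the ladder doubles from 0.6 to 1.2 to 2.4. DLT-driven expansion of those cohorts does not fit the ladder, so six would come from optional enlargement.
- A reader might see a conflict between the higher cohort labels and the limit in Section 3.1 ("4.0 mg/kg Q3W, and 6.0 mg/kg Q3W, respectively) may not receive a dose higher than 2.4 mg/kg Q3W"). The text around that sentence, and much of the amendment rationale, is redacted, so nothing can be concluded.
- A reader might call Section 6.7 a contradiction of Section 6. A specific rule can qualify a general one, and the phrase may only separate treated from untreated patients or mean the dose first received. It needs clarifying, no more.
- A reader might say that PK and response are misfiled. Sections 6.5 and 6.6 say dose level without saying assigned or received, which is an ambiguity and not a shown error.

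**Conclusion.** The point holds as a reporting gap that is cheap to close. Followed as written, the plan tabulates post-escalation adverse events, laboratory results and LVEF only under a dose lower than the one being given, by a factor of 2 from Cycle 4 (Cohorts 1 and 2) and 4 from Cycle 7 (Cohort 1).

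Those factors assume stepwise escalation at the earliest permitted time and the 2.4 mg/kg limit. The calendar shows that this is possible, not that it is likely: Section 4.2 requires an escalation meeting, written communication and Sponsor approval of each patient, all of which take time. The number affected is unknown. The count of 6 is not an absolute ceiling, because Cohorts 1 and 2 may be optionally enlarged and any cohort after Cohort 5 falls outside the stated limit. If nobody escalates, the effect is zero. No effect on the RP2D is claimed, and no view is taken on any dose or clinical rule.

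**What to change.** 1. Keep the assigned-dose tables as primary.
2. If any patient escalates, add supplementary adverse-event, laboratory and LVEF summaries by dose received at onset or assessment, with patient-cycles at each dose as denominator. A Cohort 1 patient treated for nine cycles on the schedule above would contribute three patient-cycles each at 0.6, 1.2 and 2.4 mg/kg. Let these summaries cover changes in both directions, so that reductions (Section 5.1.2.1) and restarts at a lower level after a DLT (Section 3.1.1.4) are included.
3. Show the dose at first documented response beside each responder.
4. Reword the all-summaries sentence in Section 6 and the Synopsis to allow these tables, and say that they supplement the assigned-dose tables.
5. State in Section 6.7 what treatment received means.

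The cost is wording and programming, since dosing data are already collected. The plan should name the drawbacks. A patient may appear in more than one dose column, so columns no longer add up to the number treated. Delayed or cumulative toxicity may be credited to the latest dose. Higher-dose columns will include patients selected for tolerating earlier cycles. Dose at first documented response ignores shrinkage that began at an earlier dose.
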